6.3 Medical History

Medical history will be coded using the Medical Dictionary for Regulatory Activities (MedDRA, version to be delineated in the CSR). Medical history will be presented in a data listing.

Other medical and surgical history will be summarized based on MedDRA system organ class for the ITT and Safety populations.

6.4 Inclusion and Exclusion Criteria

All inclusion/exclusion criteria deviations recorded in the electronic case report form (eCRF) will be presented in a data listing.

6.5 Treatment Compliance and Exposure

Exposure summary will be presented for the Safety population. The distribution of subjects by the total number of days on therapy, will be presented.

Treatment compliance is defined as the number of oral doses received divided by the number of doses expected (\times 100) over the time period defined by the first dose date and the last dose date. Descriptive statistics for treatment compliance and the number and percentage of subjects at least 80% compliant will be presented for the ITT population.

7 PHARMACOKINETIC ANALYSIS

7.1 Pharmacokinetic Sample Concentrations

Blood samples for PK assessments of omadacycline will be collected from all subjects at the following time points:

• Day 1: within an hour prior to Dose 1, 1.5, 2, 2.5, 3, 4, 6, 8, 12 hours (12 hour taken immediately before Dose 2);

Dose 2 administered (times relative to Dose 1); 13, 13.5, 14, 14.5, 15, 16, 24 hours post dose

- Day 2: within an hour prior to dose, 1, 1.5, 2, 2.5, 3, 4, 6 hours
- Day 3: prior to the Day 3 dose
- EOT: anytime during the visit

Individual plasma concentration of omadacycline and time deviation data for Safety Analysis Set will be presented in data listings. Plasma concentration data will be summarized by scheduled time point for the PK Analysis Set for each treatment using descriptive statistics (number of subjects, mean, SD, CV, median, minimum, and maximum). Concentrations that are below the limit of quantification (BLQ) before the first quantifiable concentration will be treated as zero for descriptive statistics. Below the limit of quantification values after the first quantifiable concentration will be set as missing and excluded for summary statistics. Mean BLQ concentrations will be presented as BLQ, and the SD and CV will be reported as not applicable, if all individual values are BLQ.

Mean (\pm SD) plasma concentrations versus nominal time will be plotted by treatment on both linear and semi-logarithmic scales for the PK Analysis Set. Individual plasma concentrations versus actual time will be plotted on both linear and semi-logarithmic scales for the Safety Analysis Set.

7.2 Pharmacokinetic Parameters

Individual plasma concentration versus actual time data will be used to estimate the PK parameters of omadacycline in plasma by standard noncompartmental methods using WinNonlin (Phoenix) validated SAS programs. For the calculation of PK parameters, BLQ values before the first quantifiable concentration will be treated as zero. Below the limit of quantification values after the first quantifiable concentration will be set as missing. Missing concentrations will be treated as missing. If consecutive BLQ concentrations are followed by quantifiable concentrations in the terminal phase, those concentrations after BLQ concentrations will be treated as missing.

Parameter	Description		
C _{max}	Maximum observed plasma concentration		
T _{max}	Time to reach maximum observed plasma concentration		
AUC ₀₋₄₈	Area under the plasma concentration versus time curve (AUC) from time 0 to 48 hours after dosing, calculated using the linear trapezoidal linear interpolation method		
AUC ₀₋₂₄	Area under the plasma concentration versus time curve (AUC) from time 0 to 24 hours after dosing, calculated using the linear trapezoidal linear interpolation method		
AUC _{last}	AUC from time 0 to the time of last quantifiable concentration (Excluding the PK concentration at EOT timepoint), calculated using the linear trapezoidal linear interpolation method		
T _{1/2}	Plasma terminal elimination half-life, calculated as $T_{1/2} = \ln (2) / \lambda_z$ λ_z = Terminal elimination rate constant calculated by linear regression of the terminal portion of the natural log-plasma concentration versus time curve. This will be calculated after third dose of administration.		

The following PK parameters will be calculated for omadacycline in plasma, if data permits:

The individual PK parameters will be presented in the data listings for the PK Analysis Set. The PK parameters will be summarized using the PK Analysis Set with the following descriptive statistics: n, mean, SD, CV, median, minimum and maximum. Descriptive statistics will include geometric mean and geometric mean CV for AUC (0-48), AUC (0-24), AUC (last) and Cmax. For individual parameters that are listed but not summarized in the descriptive statistics due to Rsq < 0.8, a footnote will be added.

7.3 Treatment Comparison

The comparison of interest is the comparative bioavailability assessment between the test, 300mg po in CABP patients, and the reference, 100mg IV in healthy subjects. The comparison will be based on 90% confidence intervals (CIs) for the geometric mean ratios (GMR) of AUC (0-48) for the two dosing regimens being within 80% and 125%.

The PK parameter data for 100mg IV in healthy subjects comes from PTK 0796-SDES-0501(n=5), PTK 0796-BEQU-0801(n=11), PTK 0796 WOIV-0703(n=12), CPTK796A2104(n=21), CPTK796A2201(n=6), PTK 0796-RENL-15102(n=8). Using the

day 1 plasma concentration profile of the 100mg IV QD dosing from these studies, a BID dosing on day 1 and a QD dosing on day 2 was simulated using the superposition principle. The simulation model-based AUC $_{(0-48)}$ characteristics for each study are shown in the table below:

Study	n	Mean ln (AUC (0-48))	SD ln (AUC (0-48))
SDES-0501	5	9.5968	0.1896
BEQU-0801	11	9.8702	0.1467
WOIV-0703	12	10.017	0.1630
A2104	21	10.043	0.1649
A2201	6	10.129	0.1752
RENL-15102	8	10.039	0.1838
Total	63	9.9800	0.2091

The 90% CI of the GMR will be formed as follows: let \bar{y} , *s*, and *n* represent the average, standard deviation, and sample of the log (AUC (0-48)) data observed in the current study. The

pooled standard deviation is $s_p = \sqrt{\frac{(63-1)0.2091117^2 + (n-1)s^2}{63+n-2}}$; the number of degrees of freedom is df = 63 + n - 2; and critical value for the CI is 95th percentile of a t-distribution, $t_{df.0.95}$. The 90% confidence interval on the log scale is

$$\bar{y} - 9.980044 \pm t_{df,0.95} s_p \sqrt{\frac{1}{63} + \frac{1}{n}} = (Lower, Upper)$$

and the CI for the GMR is $(e^{Lower}, e^{Upper}) \times 100\%$.

The following SAS code will be used:

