12.5 Primary Endpoint(s)

12.5.1 Pharmacokinetic Endpoint

The following plasma PK parameters will be determined:

- Area under the plasma concentration time curve (AUC) from time 0 to 48 hours after dosing (AUC₀₋₄₈)
- Area under the plasma concentration time curve (AUC) from time 0 to 24 hours after dosing (AUC₀₋₂₄)
- AUC from time 0 to the last quantifiable concentration (AUC_{last})
- Maximum observed plasma concentration (C_{max})
- Time to reach maximum observed plasma concentration (T_{max})
- Elimination half-life associated with the terminal slope of the semilogarithmic concentration-time curve $(T_{1/2})$

The observed omadacycline concentration-time data after an oral dosing regimen, BID on Day 1 and QD on Day 2, in CABP patients will be evaluated. 300mg administered orally is the dose that provided equivalent total exposure as measured by AUC relative to the 100mg IV dose (CPTK796-A2104). The oral bioavailability of omadacycline is 34%.

Using the superposition principle, the AUC of a single 100mg IV dose on Day 1 for n=63 healthy subjects were totaled to evaluate the AUC₍₀₋₄₈₎ of the established omadacycline IV dosing regimen (q12h on Day 1 followed by q24h on Day 2). AUC₍₀₋₄₈₎ values are then summarized and serve as the comparator for this current study. Safety and efficacy in CABP patients were demonstrated with this dosing regimen (PTK796-CABP-1200), but only sparse PK sampling was conducted. The final population PK model for omadacycline, which includes CABP patients from the PTK0796-CABP-1200 study, generated similar AUC₍₀₋₄₈₎ values for the 100mg IV dosing regimen.

The comparative bioavailability assessment between the test, 300mg po in CABP patients, and the reference, 100mg IV in healthy subjects, will be based on 90% confidence intervals (CIs) for the geometric mean ratios (GMR) of AUC₍₀₋₄₈₎ for the two dosing regimens being within 80% and 125%.

Plasma concentration data and PK parameters will be summarized by time point using descriptive statistics (number of subjects, mean, standard deviation (SD), coefficient of

variation (CV), median, minimum, and maximum). Mean and individual plasma concentration versus time profiles will be presented in figures on both linear and semilogarithmic scales. Geometric means will be included for area under the concentration-time curve (AUC) and maximum observed plasma concentration (C_{max}).

Individual plasma concentration, time deviation and PK parameters will be presented in data listings.

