12.8 Multiple Comparisons and Multiplicity

No formal comparisons are planned.

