5.1 Sample Size Determination

This study is designed to evaluate the PK profile of an oral dosing regimen, 300mg BID on Day 1 and QD on Day 2, in adults with CABP. The sample size determination is based on consideration of the precision of the estimate, GMR of AUC (0-48) for 300mg po to 100mg IV, derived from model-based simulations of omadacycline concentration data (Phase I studies).

With 20 subjects evaluable for PK population, there will be 90% probability that the 90% CIs of the GMR for AUC $_{(0-48)}$ will be within 80% and 125%. Up to 30 subjects will be enrolled so that at least 20 subjects are evaluable for bioavailability estimation.

The total number of subjects may be adjusted to ensure that there are 20 subjects evaluable for PK population.

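### The pooled-SD 90% CI in SAP 7.3 assumes equal log-AUC spread in orally dosed CABP patients and IV-dosed healthy subjects, and nothing in the documents supports that

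*SAP*

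**What the plan says.** SAP 7.3 compares exposure "between the test, 300mg po in CABP patients, and the reference, 100mg IV in healthy subjects". The reference is 63 healthy subjects from six studies, whose Day 1 IV profiles were superposed to mimic the two-day regimen; their "characteristics for each study are shown in the table below". The overall reference mean and SD of ln AUC(0-48) enter the interval as 9.980044 and 0.2091117. The SAP then sets out what the "pooled standard deviation is": that SD and the current study's SD, s, weighted into a single value by degrees of freedom. It states that "the number of degrees of freedom is df = 63 + n - 2".

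Protocol 12.5.1 gives the same criterion: the assessment "will be based on 90% confidence intervals (CIs) for the geometric mean ratios (GMR) of" AUC(0-48) lying within 80-125%. Protocol 12.8 says "No formal comparisons are planned", but the criterion remains. On size, SAP 5.1 says "Up to 30 subjects will be enrolled so that at least 20 subjects are evaluable for bioavailability estimation", and it gives a 90% probability of meeting the criterion with 20.

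**The concern.** The two groups differ in route, in population and in how AUC(0-48) is obtained (observed against superposed). Any of these could change the spread of log AUC. The nearest supporting text, in Protocol 12.5.1, says that 300 mg orally matched 100 mg IV on AUC and that a population PK model including CABP patients gave similar IV AUC(0-48). Both statements concern level, not spread. The same section says that PK sampling in CABP patients was sparse. Protocol 12.2 and SAP 5.1 give no SD.

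The unequal group sizes make the assumption matter. At n = 20 the patients supply 19 of the 81 degrees of freedom behind the pooled SD (23%). Yet at equal SDs their mean contributes 0.0500 of the 0.0659 in 1/63 + 1/20 (76%). The healthy subjects therefore largely set the SD that is applied to the patients' mean. If the patient SD is larger than 0.2091 the interval is too narrow and passing is too easy. If it is smaller, the interval is too wide. What is at stake is the verdict on the study's one stated exposure criterion.

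**Working it through.** **Inputs.** From SAP 7.3: reference n = 63, SD 0.2091117, t at the 95th percentile, limits 80% and 125% (±0.2231 on the log scale). From SAP 5.1: n = 20 evaluable, up to 30 enrolled. Assumed, because the documents give none: patient SDs of 0.15 to 0.30, normal log AUC and, except in step 5, the 63 subjects as one independent sample.

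**1. Reproduce the reference row.** From the six rows of the SAP table, the within-study sum of squares is 1.585 and the between-study sum of squares is 1.128. Then sqrt((1.585 + 1.128)/62) = 0.2092, with mean 9.9801. This agrees with the printed 0.2091 and 9.9800.

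**2. Two half-widths, n = 20, s = 0.30.**
- Pooled: s_p = sqrt((62 × 0.2091117² + 19 × 0.30²)/81) = 0.2336. Half-width = 1.664 × 0.2336 × sqrt(1/63 + 1/20) = 0.0998.
- Welch: SE = sqrt(0.30²/20 + 0.2091117²/63) = 0.0721, Satterthwaite df = 25.1, half-width 0.1231.

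With s = 0.167 the half-widths are 0.0854 (pooled) and 0.0770 (Welch, df 39.6).

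**3. Coverage and error rate.** A hand check: if the true patient SD is 0.30, the true SE is 0.0721 and the pooled half-width is about 0.0998/0.0721 = 1.38 SEs, so coverage is about 83%. At 0.15 the ratio is 0.0841/0.0427 = 1.97, so about 95%. Simulation of the pooled interval gives:

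| Patient SD | 0.15 | 0.167 | 0.19 | 0.209 | 0.25 | 0.30 |
|---|---|---|---|---|---|---|
| Coverage, n = 20 (%) | 95 | 93 | 92 | 90 | 87 | 83 |
| Pass rate at true GMR 0.80, n = 20 (%) | 2.6 | 3.3 | 4.2 | 5.0 | 6.7 | 8.5 |
| Coverage, n = 30 (%) | 93 | 92 | 91 | 90 | 88 | 85 |
| Pass rate at true GMR 0.80, n = 30 (%) | 3.3 | 3.8 | 4.4 | 5.0 | 6.1 | 7.3 |

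Under the same assumptions Welch gives 90% and 5.0%.

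**4. Where the verdict changes, n = 20.**
- Observed SD 0.167, GMR 0.867: pooled 79.6-94.4% (fails), Welch 80.3-93.6% (passes). The verdicts differ for GMRs of 0.864-0.871 and 1.148-1.157.
- Observed SD 0.30, GMR 0.90: pooled 81.5-99.4% (passes), Welch 79.6-101.8% (fails). The verdicts differ for GMRs of 0.884-0.905 and 1.105-1.131.

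**5. What Welch does not cure.** The six study means run from 9.5968 to 10.129. F = (1.128/5)/(1.585/57) = 8.1 on 5 and 57 df. The within-study SD is 0.167 and the moment estimate of the between-study SD is 0.141. Taking study as a random effect in the reference only (an assumption), n = 20:

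| Patient SD | 0.167 | 0.209 | 0.30 |
|---|---|---|---|
| Coverage, pooled / Welch (%) | 72 / 67 | 72 / 72 | 70 / 79 |
| Pass rate at true GMR 0.80, pooled / Welch (%) | 14 / 16 | 14 / 14 | 15 / 10 |

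**The case against.** The strongest objection is that the swap may not improve the decision. The figures in step 3 treat the 63 subjects as one sample, and F = 8.1 speaks against that. Under a random study effect, Welch covers less than pooled and passes more often at GMR 0.80 whenever the patient SD is below about 0.209. This stands as a limit on the remedy, but it does not rescue the pooled formula. In that model both intervals fall far short of 90%, and pooled does better at small patient SDs only because one error offsets another.

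The reach is also narrow: an open-label Phase 1b study, a protocol that disclaims formal comparisons, and verdicts that differ only in short bands of GMR. SAP 7.2 reports n, SD and geometric CV, so anyone could recompute the interval. That limits the severity. The prespecified verdict would still rest on the pooled interval, and a switch made after seeing s would be open to challenge.

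A reader might infer that the pooled interval is too lenient, because patients on oral drug could be expected to vary more. The documents give no patient SD, so they do not support this. A reader might equally infer that it is conservative, because all six single-study SDs (0.1467 to 0.1896) lie below 0.2091. That does not follow either. Those SDs come from healthy subjects given IV drug, and 0.2091 exceeds them because it also contains the between-study spread (1.128/2.713 = 42% of the sum of squares).

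**Conclusion.** The equal-SD assumption is unstated, unsupported and unnecessary, since the study estimates s itself. The size of the error depends on a patient SD that nobody can read from the documents. With one independent reference sample and n = 20, coverage is about 95% at SD 0.15 and 83% at 0.30, and the pass rate at true GMR 0.80 is 2.6% to 8.5%. At n = 30 the range is smaller, and near SD 0.21 the two intervals almost coincide. The direction is open.

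This is worth correcting before analysis. It does not show that the study's conclusion would be wrong, and it does not make Welch a true 90% interval while the differences between reference studies are ignored. The SAS code announced at the end of SAP 7.3 is not in the text I could read; the written formula is explicit.

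**What to change.** In SAP 7.3, before the data are analysed:
- Make the main interval the difference in log means ± t × sqrt(s²/n + 0.2091117²/63), with Satterthwaite degrees of freedom.
- Keep the pooled interval as a named sensitivity analysis.
- Recheck the 90% probability in SAP 5.1 and Protocol 12.2 under the new interval, stating the true GMR and patient SD assumed.
- State that the change addresses unequal SDs only, and claim 90% coverage for neither interval until variation between the reference studies is handled separately.

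The cost is one formula, its degrees of freedom, the matching code and the recheck; no new data are needed. The price in success probability at n = 20, with one independent reference sample, is:

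| Patient SD | True GMR | Pooled | Welch |
|---|---|---|---|
| 0.209 (equal) | 1.00 | 98.7% | 98.4% |
| 0.30 | 1.00 | 91% | 83% |
| 0.30 | 0.95 | 83% | 73% |

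The second row shows why the recheck is needed: at SD 0.30 and GMR 1 the pooled interval meets the stated 90% and Welch does not. At n = 30 the same case falls only from 97% to 95%.

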7.4 Analysis of EOT PK concentration data

The sample at the EOT will be collected during the patient's visit. The patients' last dose will be recorded in a dosing diary and the time of sample collection will be recorded by the site during their visit. Since patients will be outpatient at their EOT visit and must be in a fasted state when dosing, dosing is likely to occur at home prior to their site visit.

Therefore, the data collected at EOT will be used to qualitatively assesses patient's compliance by using the concentration of the EOT sample taken at the recorded time after the last dose and compared to initial dose as the clinical efficacy is an exploratory endpoint that will be evaluated. If the EOT visit is not completed on the day of last dose but within the 2-day window as specified in the protocol, then the initial dose profile will be extrapolated using the terminal elimination rate constant and will be used to make the comparison.

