8.11.1 PK Blood Collection and Processing

Blood Collection (plasma):

Blood samples will be collected and analyzed for omadacycline concentration at the following times:

- Day 1: within an hour prior to Dose 1, 1, 1.5, 2, 2.5, 3, 4, 6, 8, 12 hours (12 hour taken immediately before Dose 2);
 Dose 2 administered (times relative to Dose 1); 13, 13.5, 14, 14.5, 15, 16, 24 hours post dose
- Day 2: within an hour prior to dose, 1, 1.5, 2, 2.5, 3, 4, 6 hours
- Day 3: prior to the Day 3 dose
- EOT: anytime during the visit

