3 STUDY DESIGN

This is an open-label Phase 1b study evaluating oral omadacycline in the treatment of adults with CABP.

This study is intended to evaluate the PK of an oral dosing regimen in adults with CABP. Subjects will initiate treatment with an oral loading dose of 300 mg BID on Day 1 followed by 300 mg on subsequent days.

Following a screening period of up to 24 hours, eligible subjects will be assigned to receive 7 to 10 days of po treatment. Subjects with baseline bacteremia (i.e., confirmed from local blood culture drawn at screening) can receive up to 14 days of treatment after consultation with the medical monitor.

Subjects may receive oral treatment in either inpatient or outpatient settings, provided that all assessments can be completed at the timepoints required by protocol.

Test Article	Study Day	Study Day	Study Days
	1	2	3-10
Omadacycline	300 mg po BID	300 mg po QC	300 mg po QC

Eligible subjects will be assigned to the following treatment groups.

po = per oral, a dosing day is a 24-hour day not a calendar day

a The total duration of treatment is 7 to 10 days. Treatment duration can be extended to up to 14 days for subjects with bacteremia that, in the opinion of the investigator, requires more than 10 days of treatment.

Refer to the Schedule of Events (Appendix 1) for the summary of subject visits and assessments through end of treatment (EOT).

Subjects will return to the study site for a Post Therapy Evaluation (PTE) 5 to 10 days after the last dose of test article. A Final Follow-up visit (FFU) will be conducted within 30 to 37 days following the first dose of test article. The FFU assessment may be conducted via telephone contact or by another interactive technology for subjects who had an outcome of Clinical Success in the opinion of the investigator at EOT and PTE and had no AEs or clinically significant laboratory or electrocardiogram (ECG) abnormalities noted at or after the PTE visit. Otherwise, this assessment is to be performed with an in-person study visit.

Subjects will participate in the study for up to 37 days. Following a screening period of up to 24 hours, eligible subjects will be assigned to receive treatment. Eligible subjects will be assigned to receive 7 to 10 days of po treatment. Subjects with baseline bacteremia (i.e., confirmed from local blood culture drawn at screening) can receive up to 14 days of treatment after consultation with the medical monitor.

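### SAP 7.4 compares an end-of-treatment concentration that carries drug from earlier doses with a single first-dose profile, so this supportive compliance check has a bias of known direction

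*SAP*

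**What the plan says.** SAP 7.4 expects dosing at home before the EOT visit and says that "the data collected at EOT will be used to qualitatively assesses" compliance. The sample, at its recorded time after the last dose, is "compared to initial dose as the clinical efficacy is an exploratory endpoint that will be evaluated". If the visit falls later in the two-day window rather than on the last dosing day, "the initial dose profile will be extrapolated using the terminal elimination rate constant and will be used to make the comparison". No ratio or cut-off is given.

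SAP section 3 sets the dosing history: "Subjects will initiate treatment with an oral loading dose of 300 mg BID on Day 1 followed by 300 mg on subsequent days", and "eligible subjects will be assigned to receive 7 to 10 days of po treatment", extendable to 14 days with bacteremia. The profile after the first dose ends at 12 h, because the last sample of that interval is the "12 hour taken immediately before Dose 2". Protocol 8.11.1 gives the timing of the EOT sample as "EOT: anytime during the visit".

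Three other SAP sections bear on the point. Section 7.2 estimates the terminal rate constant after the third dose and leaves the EOT concentration out of AUC(last). Section 7.3 uses superposition to build the IV reference. Section 6.5 measures compliance separately, as doses received over doses expected.

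**The concern.** A first-dose profile contains no drug from earlier doses; an EOT sample does. The two agree only if earlier doses have washed out, which is also the pattern left by missing the doses just before the last one. A subject who took everything should lie above the reference by an amount set by the half-life.

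The SAP itself presupposes drug a day or more after a dose, since it extrapolates one dose across the two-day window. It also accepts in 7.3 that doses add up. Section 7.4 applies no such addition.

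There is a smaller gap as well. Extrapolation is provided only when the visit is not on the last dosing day, so a same-day sample more than 12 h after the dose has no defined comparator.

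At stake is how the exploratory efficacy results are read. This is the only planned check of home dosing based on a concentration.

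**Working it through.** SAP 7.4 states no figure, so there is none to reproduce. The check asks what ratio to the reference each dosing pattern would produce.

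**Inputs from the documents.** Doses at 0, 12, 24, 48, ... h. Dose count: 2 + 6 = 8 for 7 days, 2 + 9 = 11 for 10 days, 2 + 13 = 15 for 14 days.

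**Assumptions, not in the documents.** Terminal half-life T from 6 to 24 h; linear one-compartment oral kinetics; absorption rate constant ka = 1 per h.

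**Formulas.** With k = ln 2 / T, the single-dose profile is c(t) ∝ [ka/(ka − k)] × [exp(−kt) − exp(−ka·t)]. The EOT concentration t hours after the last dose is the sum of c(t + time from each taken dose to the last dose). The SAP 7.4 ratio is that sum divided by c(t). Once absorption is over, the fully compliant ratio is close to 1/(1 − 2^(−24/T)).

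**Worked case: T = 12 h, t = 4 h, 10 days.**
- k = 0.0578; c(4) = 1.0613 × (0.7937 − 0.0183) = 0.823; c(28) = 1.0613 × 0.1984 = 0.211.
- Each earlier day contributes 0.25 times the next, so all earlier doses give about 0.2106/(1 − 0.25) = 0.281. The second Day 1 dose adds a negligible amount.
- Fully compliant: 1 + 0.281/0.823 = 1.34.
- Three doses before the last missed: 1 + 0.281 × 0.25³/0.823 = 1.005.
- Last dose recorded but not taken: 0.281/0.823 = 0.34.

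**Ratio to the initial-dose profile as SAP 7.4 stands (10 days, t = 4 h):**

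| T (h) | 6 | 8 | 12 | 16 | 20 | 24 |
|---|---|---|---|---|---|---|
| Fully compliant | 1.07 | 1.15 | 1.34 | 1.56 | 1.79 | 2.02 |
| One dose before last missed | 1.00 | 1.02 | 1.09 | 1.20 | 1.34 | 1.51 |
| Three doses before last missed | 1.00 | 1.00 | 1.01 | 1.02 | 1.07 | 1.13 |
| Last dose recorded, not taken | 0.07 | 0.15 | 0.34 | 0.56 | 0.79 | 1.02 |

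With a biexponential decline instead, the fully compliant ratio is 1.05 to 1.73 at 4 h and 1.07 to 2.00 at 24 h. The direction does not change.

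**Ratio to a superposed prediction, with every scheduled dose assumed recorded as taken (same setting):**

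| T (h) | 6 | 8 | 12 | 16 | 20 | 24 |
|---|---|---|---|---|---|---|
| Fully compliant | 1.00 | 1.00 | 1.00 | 1.00 | 1.00 | 1.00 |
| One dose before last missed | 0.94 | 0.89 | 0.81 | 0.77 | 0.75 | 0.75 |
| Three doses before last missed | 0.94 | 0.87 | 0.75 | 0.66 | 0.60 | 0.56 |
| Last dose recorded, not taken | 0.06 | 0.13 | 0.25 | 0.36 | 0.44 | 0.51 |

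A single dose missed on Day 4 of 10 reads 0.99 to 1.00 against the prediction. Against the first-dose profile it also reads almost the same as full compliance.

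**The case against.** The strongest reply is that 7.4 is qualitative. It classifies and excludes no one, and a pharmacokineticist reading the data can allow for accumulation. This stands, and it limits the point. A reader might infer that the plan labels non-compliant subjects as compliant. The documents do not support that, because they contain no rule that treats a match as compliance or a high value as a problem.

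Second, the check's most direct question is whether the diary-recorded last dose was taken. At half-lives of 6 to 12 h the existing comparator answers it well (0.07 to 0.34). This stands too, but the answer weakens to 0.79 at 20 h and 1.02 at 24 h.

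Third, compliance is covered elsewhere: by dose count in SAP 6.5, reconciliation in Protocol 7.11, and return of unused product in Protocol Appendix 1. True, but none of these uses a concentration.

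Fourth, the size depends on a half-life that the documents omit. At 6 h the 7% excess would probably be lost in assay and within-subject variation.

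Fifth, the initial dose is not defined precisely, and the rate constant comes from the third dose. If the Day 2 profile were meant, a compliant subject would read 0.76 to 0.91 and the bias would reverse. The wording favours the first dose, but the SAP should say so.

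**Conclusion.** The point holds in a limited form. SAP 7.4 sets a multiple-dose sample against a single-dose profile, and no other section corrects for this. For any positive half-life a compliant subject lies above the reference. A subject who missed the doses just before a last dose that was taken lies closer to it.

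Over the assumed 6 to 24 h, with the kinetic assumptions above, the readings are 1.07 to 2.02 for full compliance, 1.00 to 1.13 with the three preceding doses missed, and 0.07 to 1.02 with the last dose untaken.

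It would be too strong to say that anyone who skips doses looks compliant. The effect concerns misses immediately before a last dose that was taken, and it shrinks when only one was missed (1.00 to 1.51). Nor does it reach the main result: AUC(0-48) does not use the EOT sample, and SAP 9.3 analyses clinical response in the ITT population with no compliance exclusion. The consequence is confined to a supportive check on exploratory data, where a correction is worthwhile and cheap.

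**What to change.** In SAP 7.4:
- State which dose provides the reference profile.
- Replace the initial-dose comparator with the subject's own predicted EOT concentration: the first-dose profile, extrapolated beyond 12 h with that subject's terminal rate constant, superposed over the recorded dose times up to the sample.
- Apply the extrapolation to same-day samples later than 12 h as well.
- Report observed/predicted for each subject. State that it tests the dosing record, since misses already recorded enter the prediction and appear in the SAP 6.5 dose count.

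The cost is SAP wording and a little more PK programming, using a method already in 7.3. The prediction is limited to subjects with an estimable terminal rate constant; 7.2 derives this after the third dose, where sampling runs to 6 h plus the Day 3 pre-dose sample. Where the time of an intermediate home dose is not recorded, the SAP should say whether the scheduled time is used. One sample still cannot reveal an isolated mid-course miss, and the SAP should say that too.
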